
 ● To evaluate the safety of baricitinib in children with JIA-U or ANA-positive uveitis 	
 ● Adverse events including serious adverse events. ● Permanent discontinuation of investigational product due to AE. ● Temporary interruption of investigational product.
Secondary for Part B (OLE) 
 ● To describe the efficacy of baricitinib in children with JIA-U or ANA-positive uveitis in the most severely affected eye and less affected eye (among the responders at Week 24) 	
 ● Number of responders through Week 284. Response is defined according to the SUN criteria as a 2-step decrease in the level of inflammation (anterior chamber cells) or decrease to zero through Week 284, in the eye most severely affected at baseline. ● Change in SUN grade of cells in the anterior chamber through Week 284 in the most severely affected eye. ● Change in SUN grade of cells in the anterior chamber through Week 284 in the less severely affected eye (if applicable). ● In patients with bilateral uveitis disease at baseline: Number of responders through Week 284, defined according to the SUN criteria as a 2-step decrease in the level of anterior chamber cells in the most severely affected eye at baseline (or both eyes if the inflammation grade is the same in both eyes) and a 1-step decrease in the level of anterior chamber cells in the less severely affected eye at baseline. ● Change in grade of flare in the anterior chamber through Week 284 in each affected eye. ● Description of inactive anterior uveitis including time to inactive anterior uveitis disease (using SUN definition) in each affected eye through Week 284. ● Number of patients who are able to taper concomitant topical corticosteroids to <2 drops per day and to 0 drops

Objectives	Endpoints
	per day. Number of patients who are able to taper concomitant oral corticosteroids to <5 mg per day and to 0 mg per day.

 To evaluate the safety of baricitinib in children with JIA-U or ANA-positive uveitis 	
 Adverse events including serious adverse events. Permanent discontinuation of investigational product due to AE. Temporary interruption of investigational product.

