5.1.3. Open-Label Treatment Period – Part B

Part B is an open-label extension period. In the previous study design (amendment d or prior), all patients who were receiving baricitinib in Part A received oral baricitinib once daily for approximately 260 weeks. Patients who were randomized to adalimumab treatment in Part A continued to receive adalimumab for approximately 96 weeks in Part B and were then switched to baricitinib for the remaining weeks. The first dose of baricitinib was given approximately 2 weeks after the last injection of adalimumab.

Since then, the protocol and study design has been modified (Amendment e). Patients receiving adalimumab will be discontinued from the study after Week 24.

Patients currently assigned to baricitinib who have completed the primary endpoint as a responder will continue receiving baricitinib until the end of study or discontinuation from the study. Investigator may consult the study team for guidance on study continuation in the event the patient is a nonresponder at the primary endpoint, but demonstrates clinically meaningful benefit from baricitinib.

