Week 8–Week 20	Reduce drops to a maximum of 2 drops/day per eye
Week 20–Week 24	No dose changes permitted
Week 24 onward (Part B)	Reduce drops at the discretion of the treating clinician to any dose, including zero

- If tapering is not tolerated during Part A or Part B, the number of drops can be increased up to the number received at screening.
- The topical steroid eye drop formulation (Maxidex, Predforte, or equivalent) should remain the same as that used at screening and will not change for individual patients throughout Part A, unless required for safety or supply issues; the formulation may be changed during Part B.

Oral corticosteroids:

- Chronic stable use of oral corticosteroids is permitted and defined as daily doses of ≤10 mg/day or 0.2 mg/kg/day prednisone equivalent, whichever is less.
- Patients must be on a stable dose for at least 2 weeks prior to screening and 4 weeks prior to baseline, and remain on the same dose throughout Part A, except for treatment of an AE.

- During Part B, oral corticosteroids may be initiated, or the dose increased, decreased, or discontinued, at the discretion of the investigator.

Intra-articular corticosteroid joint injections:

- A maximum of 8 injections are permitted per year.
- No more than 2 injections are permitted in a single session.
- No injections are permitted within 4 weeks prior to Visit 2.

Intraocular corticosteroid injections:

- Depot peri-ocular, peri-ocular or intraocular corticosteroid injections are not permitted within 30 days prior to Visit 2 or during Part A.
- Intraocular or peri-ocular corticosteroid injections are permitted during Part B at the discretion of the investigator.

Other corticosteroids

- With the exception of oral and intra-articular corticosteroids, patients should not receive other systemic corticosteroids during Part A, including intramuscular corticosteroids.
- During Part B, other systemic steroids may be administered; however, the daily dose should be ≤ 10 mg/day or 0.2 mg/kg/day prednisone equivalent, whichever is less.
- Topical, intranasal, and inhaled corticosteroids are permitted.

Analgesics and NSAIDs

- Chronic stable use of NSAIDs and analgesics is permitted. Patients must be on a stable dose for at least 1 week prior to Visit 2.
- Increases in dose and/or introduction of new NSAIDs and analgesics are not permitted during Part A, except for treatment of an AE.

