7.8.2. Special Treatment Considerations

Patients receiving baricitinib who experience a treatment failure after at least 24 weeks of treatment can have concomitant medication altered (as described in Section 7.7), but should also be considered for discontinuation from the study (see Section 8.2).

Treatment failure is defined by the presence of 1 or more of the following:

- A 2-step increase in SUN cell-activity score (anterior chamber cells) over 2 consecutive readings for patients with a baseline grade of 1+ or 2+.
- Sustained non-improvement in SUN cell-activity score for 2 consecutive readings for patients with a baseline grade of 3+ or greater.
- Only partial improvement of other ocular co-morbidity for 2 consecutive assessments.
 - Ocular co-morbidities are defined as:
 - Disc swelling and/or cystoid macular edema, as gauged clinically and confirmed by optical coherence tomography (OCT) evidence
 - Sustained raised intraocular pressure (>25 mm Hg) for more than 1 month, not responding to topical anti-hypertensives
 - Sustained hypotony (<6 mm Hg) for more than 1 month
 - Reduction in vision (LogMAR test) of 15 letters, secondary to active uveitis (excluding cataract)
 - **Note:** Patients can remain in the study in the event of cataract.
- No improvement in SUN cell-activity score over 2 consecutive readings after 6 months of therapy.
- Worsening of existing (on enrollment) ocular co-morbidity (as defined above) after 12 weeks of therapy.

8. Discontinuation Criteria

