4.2. Secondary Objectives

The secondary objectives of Study JAHW are grouped according to 2 periods defined in the study design:

Treatment Period Part A: 24 weeks

Treatment Period Part B: 260 weeks.

Baricitinib patients who complete Part A may continue to Part B, the open-label extension (OLE) period of Study JAHW. Patients on adalimumab will be discontinued after Week 24. Patients who do not continue in the OLE will have a follow-up visit (Visit 801) approximately 28 days after the last dose of the investigational product.

In particular, for Study JAHW, the secondary estimand is defined by

Population of interest: the population of interest for Part A of Study JAHW is patients who participate in Study JAHW Part A. The population of interest for Part B is patients who stay in Study JAHW Part B. Study JAHW patients are patients from 2 years to <18 years old with active JIA-U or chronic anterior ANA-positive uveitis. Analysis populations are defined in Section 6.1.1.

Variable (or endpoint) of evaluation: primary and secondary endpoints/variables are listed in [Table JAHW.4.1](#) and [Table JAHW.4.2](#). A full list of endpoints and variables is given in [Table JAHW.7.1](#) and [Table JAHW.7.2](#).

Population-level summary: the summary measure for binary variables will be proportion and the summary measure for continuous variables will be the average.

Intercurrent event(s) strategy: in Study JAHW Part A, for efficacy and health outcomes-related endpoints, the analysis population will be based on patients who have had the chance to complete the visits. In the estimand framework, for binary variables other than the primary outcome variable, the composite estimand strategy will be applied; nonresponder imputation will be applied to variables to support this strategy. The while-on-treatment strategy will be used for continuous variables, and last observation carried forward (LOCF) imputation will be used to support this strategy. For Part B, the analysis population will be based on completers for the specific analysis visit, and this method is referred as the as-observed analysis. The details of the imputation methods for the estimand and intercurrent events are described in Section 6.3. Statistical methods corresponding to each of the efficacy and health outcomes variables are summarized in [Table JAHW.7.1](#), [Table JAHW.7.3](#), [Table JAHW.7.3](#), and [Table JAHW.7.4](#).

The secondary objectives of Study JAHW are described in [Table JAHW.4.2](#).

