
To evaluate the safety of baricitinib in children with JIA-U or ANA-positive uveitis
	
Proportion of patients who are able to taper concomitant topical corticosteroids to <2 drops per day and to 0 drops per day
 
PediACR30/50/70/90/100 response rates (for patients with JIA-U)
 
Adverse events including serious AEs
 
Permanent discontinuation of investigational product due to AE
 
Temporary interruption of investigational product

Secondary for Part B (open-label extension)
 
To describe the efficacy of baricitinib in children with JIA-U or ANA-positive uveitis in the most severely affected eye and less-affected eye
	
Number of responders at Week 284: response is defined according to the SUN criteria as a 2-step decrease in the level of inflammation (anterior chamber cells) or decrease to 0 through Week 284, in the eye most severely affected at baseline.
 
Change in SUN grade of cells in the anterior chamber through Week 284 in the most severely affected eye
 
Change in SUN grade of cells in the anterior chamber through Week 284 in the less severely affected eye (if applicable)
 
In patients with bilateral uveitis disease at baseline: number of responders at Week 284, defined according to the SUN criteria as a 2-step decrease in the level of anterior chamber cells in the most severely affected eye at baseline (or both eyes if the inflammation grade is the same in both eyes) and a 1-step decrease in the level of anterior chamber cells in the less severely affected eye at baseline.
 
Change in grade of flare in the anterior chamber through Week 284 in each affected eye
 
Description of patients with inactive anterior uveitis (using SUN definition) in each affected eye through Week 284
 
Time to inactive anterior uveitis disease (using SUN definition) in each affected eye
 
Number of patients who are able to taper concomitant topical corticosteroids to <2 drops per day and to 0 drops per day. Proportion of patients who are able to taper concomitant oral corticosteroids to <5 mg per day and to 0 mg per day.

Objectives	Endpoints
To evaluate the safety of baricitinib in children with JIA-U or ANA-positive uveitis	Adverse events including serious AEs Permanent discontinuation of investigational product due to AE Temporary interruption of investigational product

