6.3.3. As-observed Analysis

For Part B of Study JAHW, the population of interest is formed by patients who complete through the analysis time as assigned. Thus, the as-observed analysis will be used for Part B. Therefore, this estimand is conditional and targets the effect of treatment conditional on completion of treatment through the time point of interest.

Only data observed at the time of interest are relevant and included in the analyses. There is no need to deal with missing data, as the population consists only of patients with observed data.

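### Part B efficacy: the SAP omits the protocol's limit to Week 24 responders, and its as-observed count takes no account of treatment escalation or of patients who leave

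*SAP*

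**What the plan says.** **Population.** In the protocol (Synopsis and Section 4, Table JAHW.5) the Part B efficacy objective carries the qualifier "among the responders at Week 24". In the SAP (Table JAHW.4.2) the objective reads "To describe the efficacy of baricitinib in children with JIA-U or ANA-positive uveitis in the most severely affected eye and less-affected eye" and stops there. SAP 4.2 adds: "The population of interest for Part B is patients who stay in Study JAHW Part B".

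**Who can be in Part B.** Protocol 5.1.3 says that under amendment (d) or earlier every baricitinib patient from Part A went on to Part B. Under amendment (e) responders continue. For the others, "Investigator may consult the study team for guidance on study continuation in the event the patient is a nonresponder at the primary endpoint", provided the patient shows meaningful benefit. SAP 5.1 says the same about amendment (e).

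**Response and analysis.** Both documents define Part B response by SUN anterior chamber cell grade alone. Protocol 10.3.1 and SAP 6.3.3 both use an as-observed analysis; the SAP says "Only data observed at the time of interest are relevant and included in the analyses" and that "this estimand is conditional and targets the effect of treatment conditional on completion of treatment through the time point of interest".

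**Permitted therapy.** Protocol 7.7 lets investigators start or increase MTX, other csDMARDs, mycophenolate and oral steroids in Part B, and adds: "Intraocular or peri-ocular corticosteroid injections are permitted during Part B at the discretion of the investigator". Under Protocol 7.8.2 a baricitinib patient with treatment failure after at least 24 weeks "can have concomitant medication altered (as described in Section 7.7), but should also be considered for discontinuation from the study".

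**The concern.** Part B is the only source of information on whether response lasts over the 260 weeks after Part A. To read a responder count that way, one must know which patients it covers and what treatment they were on when graded. The plan leaves both unsettled.

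- The two documents answer the first question differently.
- On the second, no SAP rule says how to treat a patient who met the failure definition, had other anti-inflammatory treatment added, stayed on baricitinib, and then had a clear eye. SAP 6.3 itself describes intercurrent events as including those that affect how a variable should be interpreted. The Part B strategy in SAP 4.2 deals only with completing the visit.

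At stake is the meaning of the long-term responder figure, not a pass or fail decision.

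**Working it through.** The documents give no Part B figure to reproduce, so the check is a comparison of texts followed by count arithmetic on assumed numbers.

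**1. The two populations.** Protocol: Week 24 responders. SAP: all who stay in Part B. These coincide only if no Week 24 nonresponder is in Part B, and Protocol 5.1.3 allows nonresponders in by two routes (earlier amendments, and consultation with the study team).

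**2. Direction of the population difference.** Suppose 8 of 10 observed Week 24 responders meet the response rule at a Part B visit (80%). Add m Week 24 nonresponders, of whom r respond late. The result becomes (8 + r)/(10 + m):

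- m = 2: 8/12 to 10/12 (67% to 83%)
- m = 4: 8/14 to 12/14 (57% to 86%)
- m = 7: 8/17 to 15/17 (47% to 88%)

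The count, 8 + r, can only hold or rise. The proportion falls unless r/m exceeds 80%. Both scales matter: Table JAHW.4.2 lists a number of responders, while SAP 4.2 names the proportion as the summary for binary variables.

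**3. Tracing an escalated patient.** Failure on baricitinib (7.8.2), then an injection or added immunosuppressant (7.7), baricitinib continued, SUN rule met at the next visit, data observed (SAP 6.3.3): the patient is counted as a responder. The condition in SAP 6.3.1.1 that a responder must remain on assigned treatment belongs to Part A, and would not exclude this patient anyway, because baricitinib was never stopped.

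**4. Illustration.** Assume 14 Week 24 responders enter Part B, 10 never fail and 4 fail. Of the 4, j are injected and clear, and 4 − j leave. For scale, with 20 patients and the Beta(1,1) prior, 14 is the smallest count that meets the protocol's success rule: the posterior probability that the rate exceeds 57% is 0.868 at 14/20 and 0.748 at 13/20.

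| j | As observed (10+j)/(10+j) | Escalation recoded only 10/(10+j) | Fixed denominator only (10+j)/14 | Both 10/14 |
|---|---|---|---|---|
| 0 | 10/10 | 10/10 (100%) | 10/14 (71%) | 71% |
| 1 | 11/11 | 10/11 (91%) | 11/14 (79%) | 71% |
| 2 | 12/12 | 10/12 (83%) | 12/14 (86%) | 71% |
| 3 | 13/13 | 10/13 (77%) | 13/14 (93%) | 71% |
| 4 | 14/14 | 10/14 (71%) | 14/14 (100%) | 71% |

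The as-observed 100% comes from the assumption that every injected patient clears. If one of two does not, it is 11/12 (92%). The difference from 71% is the sum of two effects, escalation and completers-only handling, and their shares depend on j.

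**The case against.** The strongest reply is that Part B sets out only to describe. SAP 7.2 gives it descriptive statistics and no success criterion, and 6.3.3 openly states that the estimand is conditional. Biologics and intraocular steroid implants stay prohibited (Protocol 7.7), and a patient who needs an excluded agent leaves the study first (8.2), so the range of escalation is limited. Concomitant medication (SAP 6.9), disposition with reasons (6.6) and steroid-taper endpoints (Table JAHW.4.2) are also planned.

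Most of this stands and lowers the severity. It does not close the gap. The stated condition is completion of treatment, which discloses dropout but not escalation. The other summaries are at group level and are not linked to any individual's response.

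It is also fair to say that the escalation gap is inferred from silence, and that counting escalation as nonresponse is one reasonable strategy among several. Nor is Part A a clean contrast: topical drops may change there, intra-articular steroid is allowed, and neither imputation rule treats added therapy as nonresponse.

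A reader might infer that every failing patient either becomes a responder through another drug or vanishes from the data. The documents do not support that. A failing patient can stay and be graded as a nonresponder, and 7.8.2 also defines failure by ocular co-morbidity, so failure and cell response are not opposites.

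**Conclusion.** Two conclusions, of different strength.

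- **Population: an inconsistency to correct.** The protocol and SAP define different Part B efficacy populations. A reader might infer that dropping the limit overstates long-term efficacy. That does not follow: Week 24 responders are the favourable subset, so adding nonresponders would usually lower the proportion, and only the raw count is bound to hold or rise.
- **Escalation and leavers: an inexpensive improvement.** Counting escalated patients as responders can only hold or raise the result. So can dropping leavers, compared with keeping them in the denominator as nonresponders. The size is unknown, because the documents give no escalation or dropout rates. It is zero if no escalated patient responds and no failing patient leaves.

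The 100% against 71% in the illustration rests wholly on assumed counts and should not be attributed to rescue alone. At j = 2, recoding escalation alone gives 83% and fixing the denominator alone gives 86%. Severity is modest.

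**What to change.** 1. In SAP 4.2, Table JAHW.4.2 and 6.3.3, restore the protocol's restriction to Week 24 responders for the Part B efficacy summaries, and list continuing Week 24 nonresponders separately.
2. Keep the as-observed count as the descriptive summary. Beside it, report a supplementary count of responders without escalation, over the fixed denominator of Week 24 responders who entered Part B. A patient counts as a nonresponder from the date of any intraocular or peri-ocular steroid injection, or any start or increase of a csDMARD (MTX included), mycophenolate or systemic steroid recorded for JIA-U.

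This needs SAP wording and one derived flag from concomitant-medication data that Protocol 7.7 already requires to be recorded. It changes nothing about permitted treatment.

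The costs are a second, lower figure and some judgement on indication where MTX or oral steroid is raised for arthritis. The fixed denominator also counts leaving for any reason against response, so the supplementary figure is a conservative companion to the as-observed count and does not replace it.

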Handling of missing, unused, and spurious data is addressed prospectively in the overall statistical methods described in the protocol and in the SAP, where appropriate. Adjustments to the planned analyses are described in the final CSR.

Missing Data Imputation

The following methods will be used to impute missing data in Part A:

Modified nonresponder imputation (mNRI):

For primary efficacy data, missing data due to lack of efficacy will be imputed as a nonresponder under mNRI. If primary efficacy data are missing for reasons other than this, available preceding data from patients with missing data will be reviewed by an independent and external Clinical Endpoints Committee (CEC), as outlined in the CEC charter. The CEC will ensure that patients with missing data are evaluated in a consistent manner. The CEC will consider the complete patient history and the reasons for the missing data, in order to determine whether responder or nonresponder status is appropriate on a case-by-case basis. Study sites should send any requested source documentation to the CEC in a timely fashion.

Nonresponder Imputation (NRI):

A patient is defined as a responder only if (i) they meet the clinical requirements for response at the predefined time and (ii) they remain on the assigned study treatment; failing either criteria by definition (i) or (ii) makes them a nonresponder.

Binary efficacy and health-outcome data, excluding the primary outcome data, will be imputed using NRI. Patients will be considered a nonresponder for the NRI analysis if they do not meet the clinical response criteria or are entirely missing the visit at the analysis time point. Patients without at least 1 postbaseline observation will also be defined as nonresponders for the NRI analysis.

Last observation carried forward (LOCF):

The LOCF method will be used for the analysis of continuous endpoints (unless otherwise stated). For patients who discontinue the study, the last nonmissing observation will be carried forward to the subsequent time points for evaluation.

The following method will be used to handle missing data in Part B:

As-observed analysis:

A summary based on observed data at each postbaseline visit will be provided. For “as-observed” analysis, only data from completers at the visit are relevant, and therefore, the analysis does not need to deal with missing data.

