6.1.1. Analysis Populations

For purposes of analysis, the following populations are defined as shown in [Table JAHW.6.1](#).

Table JAHW.6.1. Treatment Period Populations

Population	Description
Modified Intent-to-Treat population	The mITT population is defined as patients who take at least 1 dose of investigational product in part A.
As-observed population	The as-observed population is defined as the patients who complete the analysis visit as scheduled in part B.
Safety population	The safety population is defined as all patients who receive at least 1 dose of investigational product and who do not discontinue from the study for the reason 'Lost to Follow-up' at the first postbaseline visit.

Abbreviation: mITT = modified intent to treat.

Unless otherwise specified, the efficacy and health outcomes analyses will be conducted on the modified intent-to-treat (mITT) analysis set in Part A. For the efficacy and health outcomes analyses in Part B, the analyses will be conducted on as-observed data. Safety analyses will be carried out on the safety population.

In the rare situation where a patient is lost to follow-up at the first postbaseline visit but some safety data exist (e.g., unscheduled laboratory assessments) after the first dose of study drug, a listing of the data or a patient profile will be provided.

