6.3. Handling of Dropouts or Missing Data

Intercurrent events (ICH E9[R1]) are events which occur after the treatment initiation and preclude observation of a variable or affect how it should be interpreted. Examples of such events include treatment discontinuation due to death or adverse events (AEs) and loss to follow-up. This section describes 3 missing data imputation methods for handling intercurrent events. Part A utilizes modified nonresponder imputation (mNRI) and nonresponder imputation (NRI) for categorical variables and LOCF for continuous variables. As-observed analysis is used in Part B, thus the patient analysis in Part B will be based on completer of analysis visit only; no missing data imputation method will be applied for Part B.

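### Part B percentages and mean grade changes are computed on visit completers only, so children who leave because baricitinib failed drop out of later denominators

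*SAP*

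**What the plan says.** **Analysis set.** SAP Table JAHW.6.1 defines the Part B efficacy set: "The as-observed population is defined as the patients who complete the analysis visit as scheduled in part B". SAP 6.3 adds that "no missing data imputation method will be applied for Part B". SAP 6.3.3 says that "this estimand is conditional and targets the effect of treatment conditional on completion of treatment through the time point of interest", and concludes: "There is no need to deal with missing data, as the population consists only of patients with observed data". Protocol 10.3.1 gives the same rule: "only data from completers at the visit are relevant, and therefore, the analysis does not need to deal with missing data".

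**Objective.** Protocol Section 4 (Table JAHW.5) sets the Part B aim as describing baricitinib efficacy "in the most severely affected eye and less affected eye (among the responders at Week 24". The matching objective in SAP Table JAHW.4.2 lacks the restriction to Week 24 responders.

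**Route out of the study.** Under Protocol 7.8.2, a baricitinib patient with treatment failure after at least 24 weeks may have concomitant medication altered, "but should also be considered for discontinuation from the study (see Section 8.2". Under Protocol 8.2, a patient who needs an excluded therapy leaves before it starts. Protocol 7.7 lists bDMARDs among the excluded therapies.

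**Summary measures.** SAP 4.2 says "the summary measure for binary variables will be proportion and the summary measure for continuous variables will be the average". SAP 6.1 reports categorical data as counts with percentages. Most binary Part B endpoints are worded as numbers of patients, but Protocol 9.1.2 still lists the proportion of responders at Week 284, and SAP Table JAHW.4.2 lists oral-steroid tapering as a proportion.

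**The concern.** The objective asks how a group fixed at Week 24 fares up to Week 284. The analysis describes a different group at each visit, namely those still attending. Membership is linked to outcome, because treatment failure is defined in large part by the SUN cell score, which is also the Part B efficacy measure, and failure is a stated ground for considering exit.

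Part B is 260 of the 284 treatment weeks and the trial's only long-term efficacy evidence. A percentage whose denominator shrinks as failing children leave can stay flat while a substantial part of the entering group is lost. Mean SUN-grade and flare changes have the same weakness, and they have no count to fall back on. No Part B analysis keeps leavers in the denominator. In Part A, by contrast, SAP 6.3.1.1 counts a missing visit as nonresponse for every binary endpoint except the primary one.

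**Working it through.** The plan states no Part B sample size, attrition or expected response, so there is no Part B figure to reproduce.

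**1. Direction.** Let N patients enter, k leave for failure before the visit, and r respond at the visit.
- As observed: r / (N − k).
- Over all entrants, with failure exits as nonresponse: r / N.

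The first exceeds the second whenever k > 0 and r > 0. The count r is the same in both.

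**2. Illustration over five years.** From the plan: Part B lasts 260 weeks (260/52 = 5 years); success requires a posterior probability of at least 80% that response exceeds 57%, with a Beta(1,1) prior; at least 20 baricitinib patients are to be evaluable. At n = 20, 14 responders give 0.868 and 13 give 0.748, so 14 is the smallest passing count and is used as N.

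Assumed, not in the documents: 85% response among those still present at Week 284, a constant yearly failure-exit rate f, and no other exits.

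| f per year | Retained (1 − f)^5 | Remaining of 14 | As observed | Over all 14: 0.85 × (1 − f)^5 | Gap (points) |
|---|---|---|---|---|---|
| 5% | 0.774 | 10.8 | 85% | 65.8% | 19 |
| 10% | 0.590 | 8.3 | 85% | 50.2% | 35 |
| 15% | 0.444 | 6.2 | 85% | 37.7% | 47 |

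**3. Whole-patient counts.** With N = 20 and about 80% response among stayers (both assumed):
- k = 2: 14/18 = 77.8% against 14/20 = 70.0%.
- k = 4: 13/16 = 81.3% against 13/20 = 65.0%.
- k = 8: 10/12 = 83.3% against 10/20 = 50.0%.

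The as-observed figure rises from the first case to the last while the number still responding falls from 14 to 10.

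**4. Means.** Assume N = 20, stayers averaging a change of −1.5 SUN grades, and leavers with a last change of 0 or +1. The as-observed mean is −1.5 whatever k is. Over all entrants:
- k = 2: (18 × −1.5 + 2 × 0)/20 = −1.35, or (−27 + 2)/20 = −1.25.
- k = 6: (14 × −1.5 + 6 × 0)/20 = −1.05, or (−21 + 6)/20 = −0.75.

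This holds only if leavers were doing worse than stayers.

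**5. The opposite error.** Add a further 5% per year leaving for unrelated reasons and count them as nonresponders. The fixed-denominator rates in step 2 are multiplied by 0.774 and become 50.9%, 38.8% and 29.2%. The all-cause rule then lowers them by a further 14.9, 11.4 and 8.5 points.

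**The case against.** Several points on the other side stand.

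- **Disclosed and descriptive.** The SAP says openly that the Part B estimand is conditional on completion. Part B has no decision rule and no comparison. A reader might infer concealment, or a threat to the trial's conclusion. The documents support neither, since the primary analysis at Week 24 does not use this rule.
- **Counts.** The responder endpoints for Part B in the objectives tables are numbers of patients. A reader might infer that these are inflated; they are not. The problem is confined to the percentages shown with them, the endpoints still worded as proportions, and the mean changes.
- **Failures may stay.** Protocol 7.8.2 says only that discontinuation should be considered, and Protocol 7.7 allows background therapy to be started or increased in Part B. The SUN-cell failure criteria need two consecutive readings and Part B visits are about 12 weeks apart, so a relapse will normally be recorded before exit. The loss affects later visits. Some failure criteria are ocular co-morbidities and not cell grade.
- **Disposition data.** SAP 6.6 tabulates and lists discontinuations with reasons. In a trial this small, a reader could partly rebuild a denominator by hand. No planned table does this by visit, and it cannot be done for the means.
- **All-cause nonresponse errs the other way**, as step 5 of the working shows. Carrying a SUN grade forward for up to 260 weeks would be hard to defend.

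These points argue against replacing the as-observed analysis. They do not remove the mismatch between the objective's fixed group and the changing set analysed.

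**Conclusion.** The point holds as a gap in the Part B summaries. Percentages and mean SUN-grade and flare changes describe those still attending, while the protocol's objective concerns the Week 24 responders, and no supplementary analysis links the two. For children who leave because of failure, the direction for percentages is certain. For means it depends on leavers having done worse than stayers.

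The size is unknown. A reader might take the 19 to 47 point gap in the working as the expected bias. The documents do not support that: it rests on assumed exit rates, a constant 85% response among stayers and no unrelated exits. If exits were mostly unrelated to efficacy, the as-observed figures need not be too favourable. The statement that missing data need no handling should not stand, because the protocol's own provisions link failure to leaving.

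**What to change.** Keep the as-observed summary. In SAP 6.3, 6.3.3, Table JAHW.6.1 and 7.2, with Protocol 10.3.1 aligned:

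1. For each binary Part B efficacy endpoint, add a supplementary count and percentage at each visit. The denominator is all baricitinib Week 24 responders who entered Part B and have had the opportunity to reach that visit. Add a second line for all Part B entrants, including continuing nonresponders.
2. Count patients who stopped baricitinib or left before the visit as nonresponders, under the rule in SAP 6.3.1.1.
3. Show the observed n beside the fixed n, and split exits by reason: lack of efficacy or treatment failure, against other.
4. Present mean SUN-grade and flare changes with the observed n, and summarise leavers' last on-treatment values separately.
5. Remove the statement that there is no need to deal with missing data.

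The cost is SAP wording, an aligned protocol paragraph and one extra set of descriptive tables from data already collected. Counting unrelated exits as nonresponse is conservative; the split by reason makes that visible.
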